**Figure 2. Spleen tyrosine kinase inhibition in COVID-19 ([name], Generated using Biorender)**

### 22.3 Fostamatinib dose, duration, and route of administration

We will use a study dose of 150mg orally twice daily for 14 days (28 doses). This regimen was studied in the recently completed phase 2 trial in patients hospitalized with COVID-19. The dose may be modified to 100mg according to pre-defined criteria in section 22.7 (Dose Modification Considerations and Medication Interactions). Study medication will be continued as an outpatient if the patient is discharged prior to completing 28 doses. If necessary, in patients unable to swallow, tablets can be crushed until granular with an approximate particle size <2 mm, added to approximately 10 mL of water, and stirred to mix before administration through an enteral tube.

While many patients on BiPAP can safely receive oral medications, it may be potentially unsafe to administer oral medications to patients at certain times while they are receiving BiPAP therapy due to risk of hypoxemia if the mask is removed and/or risk of aspiration if an oral medication is administered and BiPAP is immediately re-initiated. Determining whether an oral medication should be given to a patient receiving BiPAP therapy is a bedside clinical decision.

The goal is to administer two doses of study medication each calendar day and approximately 12 hours apart from one another. If the time between study medication doses needs to be reduced, the recommendation is to administer two doses at least 4 hours apart from one another. If a dose of study medication is entirely skipped, a missed dose should be noted in the electronic data capture

system (REDCap). Skipped doses are not “made up” by extending the dosing period; patients should only receive study drug for a maximum of 14 days, starting with randomization.

## 22.4 Placebo

The drug product is provided by Rigel Pharmaceuticals, Inc., and consists of 2 strengths of orange film-coated, plain, bioconvex tablets. The 150 mg tablet is oval, and the 100 mg tablet is round. The tablets are supplied in white opaque high-density polyethylene bottles capped with white polypropylene child resistant closures with foil induction seals. Placebo tablets to match fostamatinib 100 mg and 150 mg will be provided by Rigel Pharmaceuticals, Inc. An unblinded pharmacist at each study site will dispense and record randomization and treatment assignment.

## 22.5 Fostamatinib-specific safety considerations and potential medication interactions

Fostamatinib has a consistent safety profile, with the most common adverse reactions ( $\geq 5\%$  and more than placebo) being diarrhea, hypertension, nausea, respiratory infection, dizziness, ALT/AST increase, rash, abdominal pain, fatigue, chest pain and neutropenia. Warnings and precautions included in the US product label include hypertension, elevated liver function tests, diarrhea, neutropenia, and embryo-fetal toxicity.

- Fostamatinib must be discontinued in case the patient becomes pregnant.
- Concomitant use with strong CYP3A4 inhibitors with fostamatinib will increase exposure to the active metabolite R406 and may result in increased risk of adverse reactions. **Therefore, patients that cannot have strong CYP3A4 inhibitors held should be excluded from the Fostamatinib arm.** Strong CYP3A4 inhibitors that should exclude patients from the fostamatinib arm include: Atazanavir, Certinib, Clarithromycin, Cobicistat and cobicistat-containing coformulations, Idelalisib, Indinavir, Itraconazole, Ketocanazole, Levoketoconazole, Lonafarnib, Lopinavir, Mifepristone, Mibefradil, Nefazodone, Nelfinavir, Ombitasvir-paritaprevir-ritonavir plus dasabuvir, Posaconazole, Ribociclib, Ritonavir, Saquinavir, Telithromycin, Troleandomycin, Tucatinib, Voriconazole. Novel strong CYP3A4 inhibitors may be released after the writing of this protocol appendix. If you anticipate the patient will require a strong CYP3A4 inhibitor that is not included in the list above, please reference this regularly updated list: <https://drug-interactions.medicine.iu.edu/MainTable.aspx>

Fostamatinib itself is a weak CYP3A4 inhibitor and will result in a modest ( $\sim 1.25$  fold) increase in CYP3A4 substrates. Medications processed (activated or deactivated) by the CYP3A4 enzyme are here referred to as CYP3A4 substrate medications. Concomitant use of CYP3A4 substrate medications with Fostamatinib will modestly decrease the processing of the CYP3A4 substrate medication. If possible, CYP3A4 substrate medications should be held or have another medication substituted for them. Due to its modest effects, concomitant use of CYP3A4 substrate medications is not an exclusion criterion for this trial. However, investigators should carefully consider inclusion of patients taking CYP3A4 substrate medications with narrow therapeutic windows and should monitor closely for toxicities.

- For a full list of CYP3A4 substrates, please reference this regularly updated list: <https://drug-interactions.medicine.iu.edu/MainTable.aspx>
- All participants who are randomized to this arm should refrain from drinking alcohol while taking study drug.

- Once discharged, WOCBP must agree to use effective contraception to not get pregnant between the first dose of study drug and 30 days after the last day of study drug.

Effective contraception is defined as:

- A tubal ligation: for many teratogenic (and mutagenic) products, tubal ligation is considered a form of contraception, not a form of surgical sterilization (e.g., hysterectomy, bilateral oophorectomy).
- An approved hormonal contraceptive such as oral contraceptives, emergency contraception used as directed, patches, implants, injections, rings, or hormonally impregnated intrauterine device (IUD).

Less effective contraception is defined as:

- A form of less effective contraception is defined as Barrier methods (such as a condom used with or without a spermicide or a diaphragm or cervical cap used with a spermicide).

## **22.6 Fostamatinib Arm-Specific Exclusion Criteria**

The following exclusion criteria differ from the master protocol criteria:

1. Randomized in another trial evaluating fostamatinib in the prior 30 days

### **Study arm exclusion criteria measured within 24 hours prior to randomization:**

1. AST or ALT  $\geq 5 \times$  upper limit of normal (ULN) or ALT or AST  $\geq 3 \times$  ULN and total bilirubin  $\geq 2 \times$  ULN
2. SBP  $> 160$  mmHg or DBP  $> 100$  mmHg at the time of screening and randomization
3. ANC  $< 1000/\mu\text{L}$
4. Patient is anticipated to require a strong CYP3A inhibitor (Atazanavir, Certinib, Clarithromycin, Cobicistat and cobicistat-containing coformulations, Idelalisib, Indinavir, Itraconazole, Ketoconazole, Levoketoconazole, Lonafarnib, Lopinavir, Mifeprostone, Mibefradil, Nefazodone, Nelfinavir, Omibitasvir-paritaprevir-ritonavir plus dasabuvir, Posaconazole, Ribociclib, Ritonavir, Saquinavir, Telithromycin, Troleandomycin, Tucatinib, Voriconazole) from randomization to 21 days post-randomization. For a full list of CYP3A4 substrates, please reference this regularly updated list: <https://drug-interactions.medicine.iu.edu/MainTable.aspx>.
5. Patient unable to participate or declines participation in the fostamatinib arm.

## **22.7 Dose Modification Considerations and Medication Interactions**

**Dose Modifications:** The following dose modifications will be utilized in patients randomized to the fostamatinib arm (active or placebo). Those patients who have doses held will only complete 14 days (up to 28 doses) of study treatment. Dosing will not extend beyond day 14. Blood pressure will be monitored daily in the hospital while on study drug up until the time of discharge.

### **Hypertension:**

[figure not shown]
Blood pressure  $> 140/90$  should be treated with antihypertensives per usual care.

**During the inpatient hospitalization:** If systolic BP remains  $> 160$  mmHg or diastolic BP  $> 100$  mmHg or higher despite antihypertensive therapy, interrupt study drug. When restarting study drug

once BP is below 160 mmHg systolic and 100 mmHg diastolic, drug dose should be reduced to 100 mg twice daily or matching placebo for the remainder of the study.

- **At the time of Hospital discharge:** Patients **still on study drug** at the time of hospital discharge will have the following study procedures performed (see [Figure 3](#)):

**Figure 3. Schematic overview of blood pressure considerations and procedures performed for patients still on study drug at the time of hospital discharge**

- 1) Those with SBP < 160 mmHg and DBP < 100 mmHg will continue on study drug at the inpatient dose and have no further BP measurements for study purposes
- 2) Those with SBP  $\geq$  160 mmHg or DBP  $\geq$  100 mmHg at the time of hospital discharge will have study medication stopped and undergo the following repeat testing:

- 1) 7 (+/-2) days after post-hospital discharge a repeat blood pressure will be obtained.
  - a. If the SBP is < 160 mmHg and DBP is < 100 mmHg no further BP monitoring will be performed for study purposes
  - b. If the SBP is  $\geq$  160 mmHg or the DBP is  $\geq$  100 mmHg a follow-up will be performed in 7 (+/-2) days after the prior visit
    - i. At the repeat visit if the SBP is < 160 mmHg and DBP is < 100 mmHg no further BP monitoring will be performed for study purposes
    - ii. At the repeat visit if the SBP is  $\geq$  160 mmHg or DBP is  $\geq$  100 mmHg study guidance will recommend BP recheck by a healthcare provider

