### **7.7.6 Assessments between hospital presentation and hospital discharge**

1. On days of study medication administration (before study administration in those arms where study drug is not an infusion)
  - a. Adverse events of any grade severity present prior to the infusion or medication administration
  - b. Start and stop (or administration time if oral) times of the infusion of the investigational agent/placebo- and restart time if medication stopped for hypotension
  - c. Starting dose of study medication administration
  - d. New adverse events of grade 3-4 severity during and after study medication administration
2. Recording of specifics of study treatment according to assigned arm
3. Daily laboratory assessments as part of routine clinical care (CBC, BMP, LFTs, PT/PTT/INR, D-dimer and CRP).

4. Daily vital signs (including blood pressure), secondary outcomes and safety assessments. In the fostamatinib arm a daily CBC and liver function tests will also be performed.
5. Study-specific blood draws (AngII, Ang(1-7), NT-ProBNP and Troponin) as indicated for each investigational agent in the Ancillary Biomarker Appendix (Appendix C: Minimum Biological Specimen collection).
6. Targeted concomitant medications administered daily in the hospital including remdesivir, Corticosteroids, antiplatelet/anticoagulation, convalescent plasma, monoclonal Ab's, antibacterial agents, antiviral agents against SARS-CoV-2, ACEI's, ARBs, beta blockers.
7. Date and time of first receipt of supplemental oxygen, high-flow nasal cannula, non-invasive ventilation, invasive mechanical ventilation, vasopressors, and extracorporeal membrane oxygenation (if applicable)
8. Date and time of final receipt of supplemental oxygen, high-flow nasal cannula, non-invasive ventilation, invasive mechanical ventilation, vasopressors and extracorporeal membrane oxygenation (if applicable)
9. Pulmonary embolism, systemic arterial thromboembolism, myocardial infarction, or ischemic stroke at hospital discharge or 28 days, whichever occurs first
10. Date and time of first ICU admission
11. Date and time of final ICU discharge
12. Data and time of hospital discharge

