### 7.7.7 Assessments following hospital discharge

Patients will be followed through 90 days following randomization. The following data will be collected:

1. Number and reason for missed doses of study drug (only for those discharged prior to completing study drug if applicable)
2. Date of death (if applicable) through day 90
3. ED visits, hospital readmissions, and use of supplemental oxygen, HFNC, NIV, IMV or ECMO after hospital discharge through day 60
4. Safety outcomes (section 5.3.4) after hospital discharge and adverse events as defined in the drug specific appendices and section 13 at day 28 and day 60 (or if discharged earlier as outlined in section 7.1)
5. New or worsening symptoms not previously present at day 28 and day 60 (or if discharged earlier as outlined in section 7.1) including fever, chills, cough, chest pain, dyspnea, headache, sore throat, congestion, runny nose, fatigue, body aches

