## 22 Appendix D: Arm 3: Fostamatinib

### 22.1 Description of active therapy

Fostamatinib is an oral spleen tyrosine kinase inhibitor FDA approved for the treatment of adult patients with chronic immune thrombocytopenia (ITP) who have had insufficient response to previous treatment. Fostamatinib is a prodrug with an active metabolite, R406. R406 is protein bound and has a half-life of 15 hours, with 80% of excretion occurring in feces and 20% excreted in urine.

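### Read literally, the fostamatinib discharge blood-pressure pathway leaves out a patient whose drug was interrupted for hypertension, never restarted, and who goes home at or above 160/100 mmHg

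*Protocol*

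**What the plan says.** All of the relevant rules are in Protocol Appendix D, section 22.7, under Hypertension. They apply to active drug and matching placebo alike.

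- **In hospital.** If systolic pressure remains above 160 mmHg, or diastolic is 100 mmHg "or higher despite antihypertensive therapy, interrupt study drug". Restart, at 100 mg twice daily or matching placebo, is foreseen "once BP is below 160 mmHg systolic and 100 mmHg diastolic".
- **At discharge, who is covered.** The lead-in limits the procedures to patients who are on study drug at that point. The figure caption repeats the limit: "procedures performed for patients still on study drug at the time of hospital discharge".
- **At discharge, branch 1.** Below 160 and below 100, the drug continues and no further study blood-pressure measurement is made.
- **At discharge, branch 2.** At or above 160 or 100, patients "will have study medication stopped and undergo the following repeat testing". The first recheck is 7 (±2) days after discharge. If pressure is still high, a second follows 7 (±2) days later. If it is high again, "study guidance will recommend BP recheck by a healthcare provider".

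No branch is written for a patient who is already off the drug at discharge.

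**The concern.** The inpatient rule itself creates the missing case. A patient whose pressure never falls below 160/100 does not meet the restart condition, so may reach discharge both off drug and hypertensive. On a literal reading, that patient is outside the only part of the protocol that schedules a blood-pressure check after discharge.

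Drug status is a poor dividing line here. Branch 2 stops the drug at discharge, so everyone who is rechecked is off drug by then. The recheck therefore asks whether pressure settles once the drug is withdrawn, and the same question is open for a patient interrupted shortly before discharge. That patient has also met a demanding inpatient criterion: high pressure despite antihypertensive treatment.

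Section 22.5 lists hypertension among the US label's warnings. What is at stake is whether persistent hypertension after discharge is measured in these patients. The efficacy analysis is not at stake.

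**Working it through.** No sample-size or error-rate figure is involved. The check traces each combination of drug status and discharge pressure through section 22.7, looks for any other rule that would schedule a reading, and works out the timing.

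**1. Scheduled blood-pressure checks after discharge, by case**

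| Drug status at discharge | Pressure at discharge | Scheduled checks |
|---|---|---|
| On drug (including restarted at 100 mg) | below 160 and below 100 | 0 (branch 1, drug continues) |
| On drug (including restarted at 100 mg) | at or above 160 or 100 | 1, or 2 if the first is still high (branch 2, drug stopped) |
| Interrupted for pressure, not restarted | below 160 and below 100 | 0 (same number as branch 1) |
| Interrupted for pressure, not restarted | at or above 160 or 100 | 0 (no branch) |

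Only the last row differs from its on-drug counterpart.

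**2. Timing of the branch 2 rechecks**

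- First: 7 − 2 = day 5 to 7 + 2 = day 9 after discharge.
- Second: earliest 5 + 5 = day 10, latest 9 + 9 = day 18.

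**3. Other places that could supply a reading**

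- Section 7.1 and Table 1 footnote 5 mention a possible visit or blood-pressure check but refer back to Appendix D.
- Section 7.7.6 item 4 requires "Daily vital signs (including blood pressure), secondary outcomes and safety assessments", which covers the hospital stay. The opening of section 22.7 also covers only the hospital stay.
- Section 7.7.7 item 4 collects "adverse events as defined in the drug specific appendices and section 13 at day 28 and day 60". That section lists no blood-pressure measurement.
- Table 1 footnote 7 schedules adverse-event and concomitant-medication contacts on days 1, 3, 7, 14, 21 and 28. Under section 7.1 these may be by phone or electronic, and no reading is required.
- Section 13.2 records hypertension as an exempt serious event when it leads to new or increased antihypertensives or to stopping study drug. It does not schedule a measurement.

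**4. The two parallel rules in section 22.7**

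- The liver rule names patients discharged off study drug with raised values as a group to be retested.
- The neutropenia rule is triggered by a neutrophil count below 1.0 × 10⁹/L at discharge, a level at which the drug should already have been discontinued.

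**5. When the omission matters most**

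Section 22.1 states that "R406 is protein bound and has a half-life of 15 hours". Assuming first-order elimination, the fraction remaining t hours after the last dose is 2^(−t/15):

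- 24 h: 2^(−1.6) = 0.33
- 48 h: 2^(−3.2) = 0.11
- 72 h: 2^(−4.8) = 0.04
- 120 h (day 5, the earliest recheck for a drug stopped at discharge): 2^(−8) = 0.004

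A patient interrupted the day before discharge still has about a third of the drug level on leaving, and so resembles a branch 2 patient. One interrupted three or more days earlier has largely washed out and has already been observed off drug in hospital. The blood-pressure effect may not follow the drug level exactly.

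**The case against.** The strongest reply is that a blood-pressure interruption is a hold. Section 22.7 foresees restarting after it and describes patients with held doses as still completing a 14-day course, whereas a liver stop is permanent. On that reading a held patient is still on the regimen, and branch 2 turns the hold into a stop with rechecks. It would also explain why the liver rule needs a separate off-drug group and the blood-pressure rule does not. This reading is possible, but the text does not state it, and sites could reasonably differ.

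The second reply is that the limit is deliberate, because an interrupted patient has already had daily off-drug readings under treatment. That is fair for early interruption. It does not cover interruption a day or so before discharge, and the protocol gives no such rationale.

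The third reply is that usual-care treatment, the scheduled contacts, exempt-event recording, and collection of emergency visits and readmissions to day 60 all continue. That is true, and the patient is not abandoned. But none of these requires a blood-pressure reading.

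Finally, the case is probably rare, and the rechecks lead only to a further recheck and then advice to see a provider. Both points stand, and they keep the concern minor.

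**Conclusion.** The concern holds as a minor gap in safety follow-up. Each affected participant has 0 scheduled blood-pressure checks after discharge, against 1 or 2 for an on-drug participant with the same reading.

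The number affected cannot be estimated, because the documents give no interruption rate. It is probably small: the case needs pressure above 160/100 despite treatment, interruption, no restart, and discharge still at or above 160/100. The arm also excludes patients above 160/100 at entry (section 22.6).

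The conclusion rests on reading the on-drug limit literally. The branches of the pathway figure could not be seen, but its caption carries the same limit. Confidence is medium for these reasons. Primary outcome, power and type I error are unaffected.

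**What to change.** In section 22.7, extend the discharge lead-in, branch 2 and the figure to patients whose study drug was interrupted or stopped for hypertension, was not restarted, and whose discharge pressure is at or above 160 systolic or 100 diastolic. For them the drug stays stopped, and the existing 7 (±2) day rechecks and provider recommendation apply. Branch 1 is unchanged. This brings in off-drug patients as the liver rule does, but only those whose blood pressure caused the interruption.

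If the intention is that a blood-pressure hold counts as being on study drug, one sentence saying so closes the gap equally well.

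The cost is a wording and figure change in the arm appendix, plus one or two blood-pressure checks of an existing type in a few more participants. The rule applies equally to active and placebo, so blinding is unaffected. Sample size and analysis do not change.

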### Hepatotoxicity:

**Inpatient monitoring:** Liver function tests (LFT's) will be checked daily during hospitalization while on study drug.

- 1) Study drug should be stopped if there is an increase in either:

- a. AST or ALT greater than or equal to 5-times the upper limit of normal at the local lab or for those with elevated AST and ALT at the time of enrollment an increase to 5-times the level at enrollment
- b. AST or ALT to greater than or equal to 3-times the upper limit of normal at the local lab AND total bilirubin to greater than or equal to 2-times the upper limit of normal at the local lab.

Elevated unconjugated (indirect) bilirubin in absence of other LFT abnormalities – continue study drug with frequent monitoring since isolated increase in unconjugated (indirect) bilirubin may be due to UGT1A1 inhibition.

**Outpatient monitoring:** Patients discharged while on study drug with AST/ALT or bilirubin elevated > 2x the upper reference limits or up trending from most recent value (but less than the inpatient stopping criteria) AND patients discharged not on study drug with either AST or ALT at least 3-times the upper limit of normal or total bilirubin at least 2-times the upper limit of normal at the time of discharge will have the following study procedures performed:

1) 7 (+/-2) days post-hospital discharge a repeat measurement of AST, ALT and total bilirubin will be obtained.

- a. Patients NOT on study drug at the time of repeat LFT measurement:

\*If these repeat measurements are less than 3-times the upper limit of normal for AST or ALT and less than 2-times the upper limit of normal for total bilirubin, then no further study procedures will be performed related to LFT monitoring.

\*If these repeat measurements are greater than 3-times the upper limit of normal for AST or ALT or greater than 2-times the upper limit of normal for total bilirubin, then a repeat measurement of AST, ALT and total bilirubin should be obtained 7 (+/-2) days later. If the AST or ALT remain above 3-times the upper limit of normal or total bilirubin is above 2-times the upper limit of normal after this repeat testing 7 days later, LFTs should be monitored per standard of care by a provider or if no provider followed-up by the study team.

[figure not shown]
- b. Patients ON study drug at the time of repeat LFT measurement:

\*If these repeat LFT measurements are below the upper reference limit of normal continue study drug to completion and no recheck is needed.

\*If these measurements remain above the upper reference limit of normal for either AST, ALT or total bilirubin but do not meet inpatient stopping criteria (defined above), continue study drug and a repeat measurement of AST, ALT and total bilirubin should be obtained 7 (+/-2) days later. If this repeat testing remains above the upper limit of normal for AST, ALT or bilirubin it should be monitored per standard care by a provider or if no provider followed-up by the study team.

\*If study drug is stopped (per inpatient stopping rules above) repeat measurement of AST, ALT and total bilirubin should be obtained 7 (+/-2) days later. If this repeat testing remains above the upper limit of normal for AST, ALT or bilirubin it should be monitored per standard care by a provider or if no provider followed-up by the study team.

Once study drug is stopped for abnormal LFT values, the study drug will not be restarted.

\*up trending is defined as a >25% increase in LFTs from the day prior

**Diarrhea:** If symptoms become severe (grade 3 or above) while the patient is hospitalized, temporarily stop study drug until symptoms resolve to mild (grade 1). When restarting, study drug dose should be reduced to 100 mg twice daily or matching placebo for the remainder of the study. Study drug should be stopped if diarrhea becomes severe in the outpatient setting.

